#### 8.1.3 Other study parameters

- Baseline characteristics
  - Demographic: age, ethnicity
  - Medical history: idiopathic thrombocytopenic purpura, bloodtype (ABO and RhD and Rhc), body-mass index
  - Obstetric history: live births, spontaneous abortions, intrauterine fetal demise, mode and GA of previous deliveries.
  - Pregnancy related: gravidity, parity, pre-eclampsia, gestational diabetes, medication, smoking, obstetric care giver
  - Delivery related: GA at birth, mode of delivery, Apgar Scores, perinatal asphyxia/fetal distress, birth weight, male/female sex, place of delivery (home, hospital primary care practice, hospital secondary care practice, tertiary hospital)

### 8.2 Randomisation, blinding and treatment allocation

For every HPA-1a negative sample, the independent technicians performing the serological HPA-1a typing will select the three consecutive HPA-1a positive samples with an adequate amount of sample available. Those will be included as positive controls and material will be stored next to the HPA-1a negative samples as well. The researchers, when collecting clinical informative, will be blinded for the results of the serological HPA-1a typing as well as the HPA-1a alloantibody detection.

### 8.3 Study procedures

#### 1. Serological HPA-1a typing

To determine the incidence of HPA-1a alloimmunisation and clinically relevant FNAIT, we will be performing a serological HPA-1a typing using routine 27th week blood samples sent to Sanquin. We want to emphasize that there will be no extra blood volume taken from the patients. There will be no change in current practice for obstetric care givers. We will only need approximately 20ul of plasma and use an HPA-1a specific monoclonal antibody for serological HPA-1a typing using a flowcytometer. Optimal assay conditions for a no lyse no wash approach will be determined. Analysis will be automated.

## 2. HPA-1a alloantibody screening

More than two weeks after estimated due date based on the GA at submission of the blood samples, these samples will be tested for HPA-1a antibodies. Plasma samples of the HPA-1a negative women will be tested for the presence of anti-HPA-1a antibodies by the monoclonal antibody immobilisation of platelets. We will compare this assay with at least two other approaches:

- Luminex assay with glycoprotein (GP) IIIa coated beads as described by Chong *et al* [15]
- Surface Plasmon Resonance analysis of antibody binding to GPIIIa immobilised on a sensor chip.

## 3. Clinical follow-up data

Clinical data, of both HPA-1a negative women and HPA-1a positive controls, concerning the pregnancy, delivery and the health of the child in the first postnatal period will be obtained by contacting the obstetric and paediatric care givers without informing them on the screening result. For retrieving these clinical data the researcher(s) will receive a list of names of included HPA-1a negative and HPA-1a positive pregnant women and their obstetric care givers without disclosing the results of HPA-1a typing or antibody screening. An exception will be made for cases in which the obstetric or paediatric care giver has a suspicion of FNAIT, resulting in blood samples being sent to the diagnostic platelet serology laboratory for complete FNAIT diagnostics. In these cases the researcher will be acquainted with the test results as well. Resulting in a more fluent contact between the researcher and health care professional, when obtaining the necessary clinical information for the study.

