### **Objectives:**

1. The main objective of this study is to assess the incidence and severity of FNAIT and bleeding complications (including ICH) among neonates.
2. To develop a screening platform, including diagnostic assay(s) to identify fetuses at high risk for bleeding complications due to FNAIT.

**Study design:** Prospective observational cohort

**Study population:** Pregnant women

**Main study parameters/endpoints:** The main study parameters are HPA-1a alloantibodies, clinically relevant FNAIT. Secondary parameters include: neonatal outcome (bleeding signs other than ICH, treatment for thrombocytopenia, morbidity).

**Nature and extent of the burden and risks associated with participation, benefit and group relatedness:** These pregnant women participate in the national antenatal screening programme for Prevention and Screening of Infectious diseases and Erythrocyte Immunisation (PSIE) and have a routine blood sampling at 27th week of gestation. We will use this blood sample to perform all necessary tests, so no additional (medical) procedures will be performed. Additionally, after delivery we collect clinical data concerning the pregnancy, delivery and the health of the child in the first postnatal period by means of questioning the obstetric health care provider.

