**4. STUDY POPULATION**

*4.1 Population (base)*  
Pregnant women.

*4.2 Inclusion criteria*  
All pregnant women, of whom routine blood samples are taken at 27 weeks gestational age (GA).

*4.3 Exclusion criteria*  
There are no predefined exclusion criteria, since we are aiming to determine the incidence in the complete pregnant population in the Netherlands.

*4.4 Sample size calculation*  
Approximately 2.1% of pregnant women are HPA-1a negative, thus 1:50 pregnancies.[1, 12] In about 12% of these women HPA-1a alloimmunisation will occur and in circa one third of these cases this will cause severe FNAIT (platelet count <50 x10^9/l), of which 10% will be suffering from ICH, or 1:12.500 pregnancies.[1] In the Netherlands we thus expect a minimum of 16 affected children annually, who could possibly suffer life-long handicaps and neurological damage.

*\* based on an enrolment of 80%, for a study period of 2 years*

Each year there are approximately 60.000 RhD and/or Rhc negative pregnant women, to be screened for red cell alloimmunisation at 27 weeks gestation. We expect a 80% enrolment, based on our experience during the OPZI-study.[13] Therefore our sample size will consist of approximately 240 new cases of HPA-1a alloimmunisation, with at least 7 and more likely 10 neonates suffering from ICH.

However, the numbers above are based on published cohorts that did not describe the natural history of HPA-1a-mediated FNAIT.[1] Identified cases of FNAIT were treated with various modalities; therefore, the true prevalence would likely be higher. A second systematic review, using data from postnatal screening studies, confirmed that attempts to assess the prevalence of neonatal FNAIT purely based on clinical evaluation of symptomatic bleeding leads to significant underestimation of the prevalence.[14] Many cases had been missed. We therefore expect to find an even higher incidence of FNAIT with adverse perinatal outcomes, possibly between 1 in 5.000 and 1 in 10.000 pregnancies. Obviously, solid estimates of these numbers are essential elements for the development and implementation of a national HPA-screening program.

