### 10.2 Secondary study parameter(s) and other study parameter(s)

*Categorical data:*

- Neonatal bleeding signs
- Neonatal treatment of thrombocytopenia
- Neonatal morbidity: need for other treatments, congenital abnormalities, causes of increased bleeding tendency
- Demographic: ethnicity
- Pregnancy related
- Delivery related: Apgar scores, mode and place of delivery, fetal distress, sex
- Obstetric and medical history

*Continuous variables:*

- Laboratory findings neonate: platelet count, haemoglobin level, CRP
- Neonatal morbidity: days in hospital
- Maternal characteristics: age
- Delivery related: GA at birth, birth weight
- Medical history: BMI

*Further specification of variables can be found in chapter 8.1.*

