### **11.4 Benefits and risks assessment, group relatedness**

Screening programs require a careful balance between benefit and potential harm. Women receiving the message that they are among the 2% HPA-1a negative women, and therefore at risk for bleeding in their child, obviously will worry about adverse outcome until they are reassured by other testing, or ultimately by the birth of a healthy child. Therefore nor the participating pregnant women, nor the obstetric caregiver will be informed about the serological HPA-1a typing results. Also, we decided to perform the antibody detection test after birth. Thus no additional information can be known that would otherwise change the management of the current pregnancy, according to the Dutch Guidelines. Consequently, there will be no direct benefit for the pregnant women during this pregnancy.

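### Neonatal laboratory values and internal bleeds are seen only where routine care looked for them, so the laboratory group tests are selected and the bleeding incidence is a clinically detected minimum

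*Protocol*

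**What the plan says.** Section 8.3 (item 3) says that clinical data for HPA-1a negative women and HPA-1a positive controls "will be obtained by contacting the obstetric and paediatric care givers without informing them on the screening result". The Summary describes this follow-up as collected "by means of questioning the obstetric health care provider"; sections 3 and 8.3 add paediatric care givers. The routine week-27 sample serves for all study tests, "so no additional (medical) procedures will be performed" (Summary). Section 11.4 explains that neither the women "nor the obstetric caregiver will be informed about the serological HPA-1a typing results". Where a caregiver suspects FNAIT, samples go for full diagnostics, and "In these cases the researcher will be acquainted with the test results as well" (8.3).

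Section 8.1.1 names two main parameters: the incidence of HPA-1a alloantibodies and that of clinically relevant FNAIT, a composite of perinatal death, ICH and haemorrhage in an internal organ. Among the continuous secondary variables, 10.2 lists "Laboratory findings neonate: platelet count, haemoglobin level, CRP". Continuous variables are to be compared by t-test or Mann-Whitney test with two control groups: HPA-1a negative women without alloantibodies and HPA-1a positive women.

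On expected numbers, 4.4 cites a review showing that "attempts to assess the prevalence of neonatal FNAIT purely based on clinical evaluation of symptomatic bleeding leads to significant underestimation of the prevalence". It continues: "We therefore expect to find an even higher incidence of FNAIT with adverse perinatal outcomes", possibly 1:5,000 to 1:10,000.

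**The concern.** Nothing in the protocol makes a neonatal blood count or cranial imaging a study measurement. Whether one exists depends on a caregiver who does not know the mother's HPA-1a type or antibody status. This has two consequences.

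First, a laboratory comparison between alloimmunised cases and controls uses only infants in whom someone saw a reason to draw blood. Selection then depends on health in both groups, and the difference and its p-value do not estimate the effect of alloimmunisation.

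Second, an ICH or organ bleed that is silent or not imaged counts as no event. The reported bleeding incidence is then a minimum, and in the assay work such infants would be classed as low risk. If a count at or below the published rate were read as the true incidence, it could be taken to refute the higher rate that 4.4 expects. Incidence and severity are the Summary's main objective, and the result is meant to inform a decision on national screening.

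**Working it through.** **1. What each result depends on**

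- HPA-1a alloantibodies: stored plasma of all HPA-1a negative women is tested, whatever the symptoms (8.3, item 2). No dependence on caregiver testing.
- Perinatal death: reported by caregivers, and no test is needed to know of it. Should be largely captured.
- ICH and organ haemorrhage: known only if symptoms or imaging revealed them.
- Platelet count, haemoglobin, CRP: known only if routine care measured them.

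**2. The plan's own numbers (inputs from 4.4)**

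- Women: 60,000 × 2 years × 0.80 = 96,000
- HPA-1a negative: 96,000 × 0.021 = 2,016
- Alloimmunised: 2,016 × 0.12 = 241.9 (protocol: about 240)
- Severe: 241.9 / 3 = 80.6
- ICH: 80.6 × 0.10 = 8.1, or 96,000 / 12,500 = 7.7 (protocol: at least 7)

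The protocol's more likely figure of 10 ICH needs a rate of 10 / 96,000 = 1:9,600 with every ICH detected.

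**3. Adding incomplete detection**

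Observed ICH = 96,000 × true rate × s, where s is the share of true ICH that routine care detects. The protocol gives no value for s, so 80% and 50% are assumptions.

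| True rate | s = 100% | s = 80% | s = 50% |
|---|---|---|---|
| 1:12,500 | 7.7 | 6.1 | 3.8 |
| 1:10,000 | 9.6 | 7.7 | 4.8 |
| 1:5,000 | 19.2 | 15.4 | 9.6 |

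At the lower end of the forecast, 80% detection gives the same count as the published rate with full detection, and 50% gives fewer. At 1:5,000 even 50% detection leaves the count above 7.7. Two simplifications apply. The forecast concerns adverse outcomes in general and is used here as an ICH rate. The published 1:12,500 is taken at face value, since its own completeness is not given.

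**4. Illustration for platelet counts**

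Take 240 alloimmunised, of whom 80 are severe (one third, from 4.4) and 160 are not. Assume that 10% of the non-severe infants get a count (160 × 0.10 = 16) and that 30%, 60% or 90% of the severe ones do. These rates are assumptions.

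| Severe infants tested | With a count | Severe / tested | Severe / all 240 |
|---|---|---|---|
| 30% (24) | 40 | 60% | 10% |
| 60% (48) | 64 | 75% | 20% |
| 90% (72) | 88 | 82% | 30% |

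The true share is 33% in every row. Tested infants alone overstate it, and all infants as denominator understate it. Without a record of who was tested, a reader cannot judge how wide the gap is.

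**The case against.** The strongest reply is that 4.4 warns about something else, namely finding FNAIT only through symptomatic bleeding. Here every HPA-1a negative woman is antibody-tested, so a death or bleed that no caregiver linked to FNAIT can still be attributed. Section 4.4 also gives a second reason for expecting more cases: the earlier cohorts were treated, whereas this study follows the natural course. This stands. A reader might infer that the protocol contradicts itself by warning of underestimation and then predicting a higher incidence, but the documents do not support that. What remains is the narrower gap of bleeds that nobody saw or imaged.

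A reader might also infer that the protocol treats platelet counts as measured in every infant, or that tested controls are necessarily the ill ones. The protocol says neither. It is silent on availability, and missing-data handling may sit in an SAP that is not shown. But the data sources and the named tests are fixed in this protocol, and no SAP can recover whether a count or scan was done if that was not collected.

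Finally, withholding the results is a deliberate choice, explained in 11.4, and is not criticised here. Severe thrombocytopenia is not itself an endpoint in 8.1; platelet count is.

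**Conclusion.** The point holds in a limited form. The between-group tests on platelet count, haemoglobin and CRP would probably compare infants selected for a clinical reason to test, and their p-values should not be read as effects of alloimmunisation. The ICH and organ-haemorrhage part of clinically relevant FNAIT is a clinically detected, minimum incidence. It would be too strong to call the whole primary result a minimum, because the alloantibody incidence is not affected and perinatal death should be largely captured.

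The forecast in 4.4 is over-confident rather than contradictory. With an assumed detection of 50-80%, a true 1:10,000 gives 4.8-7.7 observed ICH, no more than the 7.7 expected at 1:12,500. That size rests entirely on the assumed detection.

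A reader might also put the effect as severe thrombocytopenia appearing in 7-20% of alloimmunised cases instead of 33% (an assumed 20-60% of 80.6 severe cases, or 16-48, divided by 242). The documents do not support this as a measured bias. The testing rate has no anchor in them, the protocol does not plan that ratio, and its own severe share runs from 10-30% (Summary, section 1) to one third (4.4), which largely overlaps 7-20%.

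**What to change.** - **8.1.1 and 10.1:** call the ICH and organ-haemorrhage result the clinically detected (minimum) incidence. Leave the alloantibody wording as it is.
- **4.4:** keep the forecast, and add that it refers to true incidence and that the observed count may be lower if bleeds go undetected.
- **8.3, item 3:** in the existing caregiver contact, record whether a platelet count was done (yes/no), and whether cranial imaging was done (yes/no) and why.
- **10.2:** report the proportion tested per group and describe platelet count, haemoglobin and CRP among those tested. Treat any between-group p-values for them as descriptive.
- **Severe thrombocytopenia, where reported:** give a range, with untested infants counted first as not severe and then as having the same rate as tested infants. The second figure is an upper limit only if tested infants are at least as likely to be severe as untested ones, so say so.

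The cost is two extra data items, some wording, and the p-values for three laboratory variables lost or downgraded to descriptive. No additional neonatal testing is proposed, and no care changes.

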### 3. STUDY DESIGN

We will perform an observational prospective cohort study, during a period of two years. All pregnant women, participating in the nationwide prevention program organized by the RIVM to screen for red cell alloimmunisation in Rhesus D (RhD) and Rhesus c (Rhc) negative pregnant women, will be informed about participation in our study. The RIVM was consulted during the development of the study design and consented under certain conditions. An informed consent procedure will be applied, in which the RhD and Rhc negative pregnant women will be informed by their obstetric caregivers using our information flyers and are subsequently given the opportunity to either accept or object to participation. See chapter 11.2 for further specification. Regardless, all blood samples of RhD and Rhc negative pregnant women will be tested, because the blood sample for HPA-1a typing is needed to be fresh. These data will be quarantined. The HPA-1a typing will be performed using the blood sample that is already send to Sanquin.

Figure 1 - Flow chart of study design

Nothing will be changed about the procedure as it currently is, regarding to the logistics as well as the volume of blood drawing itself. Blood samples from the expected 2.1% HPA-1a negative women and a control group consisting of 3 random HPA-1a positive women for each HPA-1a negative woman will be stored.

When receiving an objection to participate these samples will be deleted from storage as well from the database. After delivery, the stored blood sample will be used to test for the presence of HPA-1a alloantibodies. Clinical follow up data concerning the first postnatal period will be obtained by directly contacting the obstetric and paediatric care givers. After obtaining clinical information the depicted samples can be used to determine the diagnostic accuracy of several experimental assays that may be used to discriminate high risk cases, who will develop clinically relevant disease, from low-risk cases. An overview of the study design is displayed in **Figure 1**.

[figure not shown]

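### Section 8.3 lifts the blinding promised in 8.2 for women with suspected FNAIT while their outcomes are still being collected, and Sections 3 and 8.2 give different rules for choosing controls

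*Protocol*

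**What the plan says.** Section 8.2 states the blinding rule without qualification: "The researchers, when collecting clinical informative, will be blinded for the results of the serological HPA-1a typing as well as the HPA-1a alloantibody detection".

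Section 8.3, item 3 (clinical follow-up data), first repeats the principle: the researcher gets a list of included women and their care givers, without typing or antibody results. It then departs from it: "An exception will be made for cases in which the obstetric or paediatric care giver has a suspicion of FNAIT", where this leads to samples being sent for full FNAIT diagnostics. The consequence is "In these cases the researcher will be acquainted with the test results as well". The reason given is "Resulting in a more fluent contact between the researcher and health care professional, when obtaining the necessary clinical information for the study".

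Two sections describe how controls are chosen. Section 3 speaks of "a control group consisting of 3 random HPA-1a positive women for each HPA-1a negative woman". Section 8.2 says that the typing technicians "will select the three consecutive HPA-1a positive samples with an adequate amount of sample available".

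Section 10.2 compares outcomes with two groups, HPA-1a negative women without alloantibodies and HPA-1a positive women, and works an example for ICH.

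**The concern.** The blinding exception takes effect during outcome collection, and its declared purpose is to make that collection go more smoothly in the cases concerned. Its trigger is not neutral. Section 1 says that affected children are at present diagnosed only once clinical symptoms appear, so suspicion depends on the very signs being recorded. A researcher who knows the serology may ask further, obtain more records, or read an ambiguous finding differently.

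At stake is the controlled comparison. If bleeding is sought harder where FNAIT is suspected, and suspicion is commoner among antibody-positive women, the contrast with the comparison groups is overstated. Section 4.4 itself warns that reliance on clinically evident bleeding misses many cases; unequal effort works against the study's aim of correcting that.

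The control-selection conflict is a separate and smaller matter. Random and consecutive sampling are different procedures, and the condition on sample volume is written for controls only. A reader cannot tell which rule will be followed.

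**Working it through.** **Blinding, sections side by side.**

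- 8.2: collectors of clinical data are blinded to typing and antibody detection; no exception and no cross-reference.
- 8.3, item 3: blinded, except where FNAIT is suspected and samples are sent; there the researcher learns the results.
- Timing: the stated reason concerns obtaining clinical information, so disclosure comes before collection is complete.
- Who is covered: any woman on the list whose care giver suspects FNAIT, in either group.

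**Which outcomes are exposed (8.1.1 and 8.1.2).** Perinatal death is hard to miss or to over-call. ICH and internal organ haemorrhage depend more on whether they were looked for. Petechiae, haematoma, purpura and mucosal bleeding depend most on how closely one asks.

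**The protocol's own figures, reproduced.** Inputs from Sections 3 and 4.4: 60,000 women a year, 2 years, 80% enrolment, 2.1% HPA-1a negative, 12% alloimmunised, one third severe, 10% of those with ICH.

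- Enrolled: 60,000 × 2 × 0.80 = 96,000
- HPA-1a negative: 96,000 × 0.021 = 2,016
- HPA-1a positive controls: 3 × 2,016 = 6,048
- Alloimmunised: 2,016 × 0.12 = 241.9 (stated: about 240)
- ICH: 241.9 ÷ 3 × 0.10 = 8.1 (stated: at least 7, more likely 10)
- Section 10.2 table, 10/120 against 1/360: relative risk 0.0833 ÷ 0.00278 = 30; two-sided Fisher p = 6.2 × 10⁻⁶ (stated: 30 and p < 0.0001)

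All of these reproduce.

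**How sensitive the contrast is to a few events.** The shifts below are assumed, to show scale; they do not estimate the bias. The denominators of 120 and 360 are kept as printed.

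| ICH, antibody-positive | ICH, controls | Relative risk | Fisher p |
|---|---|---|---|
| 10 | 1 | 30 | 0.000006 |
| 10 | 2 | 15 | 0.00003 |
| 10 | 3 | 10 | 0.0001 |
| 7 | 2 | 10.5 | 0.0012 |
| 6 | 5 | 3.6 | 0.033 |

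The finding of a difference survives every row at the 5% level. The relative risk does not hold steady: one more event found in controls halves it.

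**Control selection, sections side by side.** Section 3: three random HPA-1a positive women per HPA-1a negative woman. Section 8.2: three consecutive HPA-1a positive samples, subject to enough material. No text says that one is shorthand for the other.

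**The case against.** The best defence is that 8.2 gives a general rule and 8.3 an openly declared exception, with a reason. The test results may mean only the clinical diagnostics, which the care giver who sent the samples would be expected to have; a researcher speaking to that care giver could hardly stay blind. The primary parameter is an incidence, and 10.2 introduces the controlled comparison for secondary parameters.

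Part of this stands. The exception is declared, and blinding in suspected cases can never be perfect. But 8.2 does not mention the exception, the worked example in 10.2 is ICH, a component of the primary endpoint, and a possible leak through the care giver is no reason to plan disclosure before the outcome is recorded.

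A reader might infer four stronger claims. The documents do not support them.

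- **That unblinding never happens in controls.** The trigger is suspicion plus samples sent; item 3 covers HPA-1a negative women and HPA-1a positive controls alike.
- **That most primary events would be collected unblinded.** No share is given or derivable, and 4.4 says that many cases are missed clinically.
- **That list order reveals the HPA-1a negative woman.** No order is stated. Even in sample order, with each HPA-1a negative woman followed by her controls, deletion of objectors breaks up sets: at an assumed independent 80% consent, 0.8⁴ = 41% stay intact, although she would still come first in 0.8 ÷ (1 − 0.2⁴) = 80% of non-empty sets. Order would show typing only, and about 12% of HPA-1a negative women are expected to have antibodies.
- **That the experimental assays are read with knowledge of outcome.** Section 3 places them after clinical information is obtained, which is timing only. Section 12.1 already codes the samples, and reader masking may be set out in a document not shown.

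Nor does any passage link sample volume to outcome, so the volume condition is a matter for consistency, not a demonstrated bias.

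**Conclusion.** The point holds in two parts. First, the plan as written discloses test results to the outcome collector, on an outcome-related trigger, before collection is complete, and this conflicts with the unqualified promise in 8.2. It can make ascertainment of ICH, organ haemorrhage and minor bleeding signs differential in the 10.2 comparison. Second, the two control-selection rules are inconsistent and must be reconciled.

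The size of the bias cannot be derived: the protocol gives neither the number of suspected cases nor how far collection would differ in them. The judgement rests on suspicion being commoner where bleeding signs occur, and on knowledge of the result affecting how those signs are sought or read. With about 8 to 10 ICH cases expected, a few events would move the estimated relative risk a good deal, though probably not the finding that a difference exists. The stated sample size and p-value are unaffected. This should be corrected, but it does not undermine the design.

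**What to change.** - **8.3, item 3:** for every woman, suspected cases included, complete and lock the same standard outcome form before the laboratory discloses any result to the researcher. Record later details in a separate field that is not used for the controlled comparison.
- **8.2:** state the exception and refer to 8.3.
- **Section 3 and 8.2:** state one control-selection rule in both places, and say whether the volume condition applies to both groups.
- **8.3 and 12.1:** say that the contact list is released in random order. This is a no-cost safeguard, since no order is given.

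The cost is procedural wording and a short delay in disclosure to the researcher only, in the suspected cases. Clinical diagnostics are untouched and no extra staff are needed. The remaining weakness is that a care giver may mention the diagnosis before the form is locked; the form could carry a tick box for this, so that its frequency can be reported.
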